9.2 Sample Size and Accrual

As this is primarily a safety study, we should be able to ascertain serious AEs with 15patients/group. We have already identified approximately 15 patients who meet screening criteria for enrollment, thus accrual should not be problematic.

10. DATA COLLECTION, SAFETY MONITORING, ADVERSE EVENTS REPORTING

10.1 Records Retention

The period of paper and electronic record retention will be consistent with the record retention policies of the University of Texas Health Science at Houston and the applicable regulatory agencies for the trial, including the FDA and OHRP. However, in certain instances, documents should be retained for a longer period if required by the applicable regulatory agency.

10.2 **Quality Assurance**

The study will be conducted according to Good Clinical Practice (GCP) guidelines, the Declaration of Helsinki, US 21 Code of Federal Regulations (CFR) Part 50 – Protection of Human Subjects, and Part 56 – Institutional Review Boards.

All pediatric research at the University of Texas Health Science Center at Houston is subject to random audits throughout the year by a monitor from the institution's IRB as well.

Independent Medical Monitor (IMM) 10.3

A monitor from Juno Research Inc. will serve as the IMM. Juno Research has provided this service for previous TBI trials at UT Health and Children's Memorial Hermann Hospital. The IMM will provide oversight of the protocol and ongoing study activities with an emphasis on data integrity and quality assurance, protocol adherence, study participant safety issues, and in particular the review of AEs and SAEs. In addition to data quality, the IMM will review consent forms and regulatory documents as part of the monitoring plan.

The IMM will make recommendations to the PI regarding continuation, modification or conclusion of the trial, while protecting the confidentiality of the trial data. In the unlikely event of unexpected or unduly high rate of SAEs, the IMM will notify the MSM, the DSMB, and the PI of these findings. The IMM will review the medical record and data collected following post-infusion Day 21 of the first subject. Thereafter, they will review after subject 5, and each subsequent fifth subject, unless another visit is recommended by the MSM, DSMB, FDA or IRB.

10.4 Medical Safety Monitor (MSM)

[name] will serve as the MSM. [name] is faculty for the Department of Hematology/Oncology-Bone Marrow Transplantation at The Methodist Hospital and the Center for Cell and Gene Therapy in Houston, Texas. [name] is experienced in the field of cellular therapies, including bone marrow harvest and transplantation. In addition, he is experienced in the release criteria of cellular products and potential AEs related to infusion toxicity. He has served on previous DSMBs, including having served as the DSMB Chair of the Phase 1 Pediatric TBI stem cell trial. [name] primary responsibility will be to review SAEs in real time to ensure good clinical practice and to quickly identify safety concerns. He may suggest protocol modifications to prevent the occurrence of particular adverse events. He will remain blinded to the treatment assignment, unless the DSMB approves unblinding, and will review SAE reports following post-infusion Day 21 of each subject (if applicable) for submission to the PI,

DSMB, FDA and IRB, and prior to each DSMB meeting. [name] is not affiliated with UT Health in any manner, nor does he practice within the Memorial Hermann Hospital System. The MSM will work in conjunction with the IMM and the DSMB to ensure the safety of the intervention in this trial.

All reports of hospitalization due to infection or neurological events, and all subject deaths will be reported to the MSM.

10.5 Data Safety and Monitoring Board (DSMB)

Although this is a single site, relatively small sample size study, we plan to use a DSMB instead of a SMC-monitored approach. DSMB membership, responsibilities, meetings, and DSMB reports are described in the DSMB Charter (Appendix C).

10.6 Adverse Experience Reporting

10.6.1 Overview

All safety data will be reviewed by the Medical Safety Monitor (MSM) in real time, as well as, the Independent Medical Monitor (IMM) at regular monitoring visits according to the monitoring plan. Based on the data, the MSM may suggest protocol modifications to prevent the occurrence of particular adverse events. The data will also be reviewed by the DSMB at bi-annual meetings, or on an as-needed basis if required. The DSMB can recommend protocol modifications and/or study termination because of safety findings. All FDA, OHRP and the University of Texas Health Science Center at Houston IRB requirements for reporting adverse experiences will be followed.

10.6.2 Definitions [21CFR310.305]

10.6.2.1 Adverse Experience

Any adverse event associated with the use of a drug or biologic in humans, whether or not considered drug related. For this protocol, temporally association with the use of the cellular product will be considered.

10.6.2.2 Disability

A substantial disruption of a person's ability to conduct normal life functions.

10.6.2.3 Life-Threatening Adverse Experience

Any adverse experience that places the patient, in the view of the initial reporter, at *immediate* risk of death from the adverse experience as it occurred, *i.e.*, it does not include an adverse experience that, had it occurred in a more severe form, might have caused death.

10.6.2.4 Serious Adverse Experience

Any adverse experience that results in any of the following outcomes: Death, a life-threatening adverse experience, inpatient hospitalization or prolongation of existing hospitalization, a persistent or significant disability/incapacity, or a congenital anomaly/birth defect. Important medical events that may not result in death, be life-threatening, or require hospitalization may be considered a serious adverse drug experience when, based upon appropriate medical judgment, they may jeopardize the patient or subject and may require medical or surgical intervention to prevent one of the outcomes listed in this definition.

10.6.2.5 Unexpected Adverse Experience

Any adverse experience not listed in the current labeling for the drug or biologic product. This includes events that may be symptomatically and pathophysiologically related to an event listed in the labeling, but differ from the event because of greater severity or specificity. "Unexpected," as used in this definition, refers to an adverse experience that has not been previously observed.

10.7 Recording Adverse Experiences

Safety data will be recorded on CRFs designed for this purpose. Adverse experiences will be collected from the time of randomization until completion of study visits or until 30 days after premature withdraw from the study. If an abnormal value or result is determined by the investigator to be clinically significant and/or temporally related, the adverse experience will be recorded on the appropriate CRF.

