1.1 Primary Objective

To determine if autologous cells using either BMMNCs or hUCBs are safe to administer in children with CP.

Primary safety outcome measures:

- 1. In-hospital infusion toxicity: pulmonary and hepatic function; new seizures, hemorrhagic lesions or ischemic lesions on imaging.
- 2. Long-term safety: development of new mass lesions or other pathological structural changes; worsening neurological status.

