8.2 Withdrawal of Individual Subjects

The Principal Investigator will make every reasonable effort to keep each subject in the study through the 2 year visit. If a subject withdraws from the study, the reason for withdrawal must be documented in the study chart. Possible reasons for withdrawal include: adverse experiences, protocol deviation, including non-compliance, lost to follow-up, discretion of investigator or DSMB, or other regulatory agency/body. Subjects will be withdrawn from the study immediately if any of the following occur:

- a. The subject or their parent(s)/LAR requests withdrawal from the study.
- b. The investigator believes it is in the best interest of the subject.
- c. There is clinically significant deterioration of the subject's medical status that warrants termination from the study.
- d. There are clinically significant abnormal laboratory results that warrant termination from the study.

[figure not shown]

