8.3 Withdrawal of Subject from the Study Following Adverse Events

The investigator must apply his clinical judgment to determine if an adverse event (AE) is of sufficient severity to require that the subject should immediately be withdrawn from the study. If the withdrawal from the study is due to an AE, the subject should be given appropriate care under medical supervision until the symptoms of the AE resolve or his/her condition becomes stable. Subsequent review by the MSM, DSMB, or IRB may also result in the suspension of further trial enrollment (see Stopping Rules). A subject (or Parent/LAR) may also voluntarily withdrawal from treatment due to what he/she perceives as an intolerable AE, or for any other reason. If voluntary withdraw is requested, or if withdrawal occurs for any reason, the subject should be asked to continue (at least limited) scheduled evaluations, complete an end-of-study evaluation, and be given appropriate care under medical supervision until the symptoms of any AE resolve or the subject's condition becomes stable.

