8.4 Procedures for Handling Withdrawals

In case of early withdrawal, subjects will be asked to continue (at least limited) scheduled evaluations and to complete an end-of-study evaluation which includes all scheduled exams, procedures, and laboratory tests as if it is the 12 Month visit; and should be given appropriate care under medical supervision until the symptoms of any AE resolve or the subject's condition becomes stable. If the subject is unwilling or unable to complete visits, he/she will be asked to return for the end-of-study visit and then should be followed through telephone calls by the coordinator. Subjects who do not complete study treatment or all follow-up will be asked to provide the same data as subjects who withdraw.

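### Adverse event recording stops 30 days after withdrawal while withdrawn children are still to be seen or telephoned, so new or recurrent late events have no clear place in the data

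*Combined protocol and SAP*

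**What the plan says.** All references are to the combined protocol and SAP.

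- **Recording window (10.7).** Adverse experiences are collected from randomization "until completion of study visits or until 30 days after premature withdraw from the study".
- **Reasons for withdrawal (8.2, 8.3).** One trigger for immediate withdrawal in 8.2 is: "There is clinically significant deterioration of the subject's medical status that warrants termination from the study". Clinically significant laboratory abnormalities are another. Section 8.3 has the investigator judge whether an adverse event "is of sufficient severity to require that the subject should immediately be withdrawn from the study".
- **Follow-up after withdrawal (8.3, 8.4).** After early withdrawal, "subjects will be asked to continue (at least limited) scheduled evaluations and to complete an end-of-study evaluation". The content of that evaluation is set "as if it is the 12 Month visit". A child who cannot or will not complete visits is asked back for it and "then should be followed through telephone calls by the coordinator". Care continues until any adverse event has resolved or the child is stable.
- **Objective (1.1).** The second primary safety measure is "Long-term safety: development of new mass lesions or other pathological structural changes; worsening neurological status". Follow-up runs to 2 years (sections 3 and 8.2).
- **Analysis (9.1.1).** Kaplan-Meier and other survival methods are planned for time to SAEs, AEs and death, using the timing of withdrawals. No rule is given for events after withdrawal or for withdrawal prompted by a safety problem.

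**The concern.** Staff are told to stay in contact with withdrawn children, but the recording rule appears to close after a month. A coordinator who learns at month 14 of a new seizure disorder in a child withdrawn at month 6 has no clear instruction to enter it.

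Three features make this matter. Long-term safety is part of the primary objective. The treatment is one infusion, so leaving the study does not end exposure. And the reasons for leaving overlap with what is being measured: clinically significant deterioration may be a worsening neurological state. If children who are doing badly leave more often and are then recorded for only 30 more days, the remaining data could understate late harm. With about 20 children given cells at baseline, one or two unrecorded events would change the estimate noticeably.

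**Working it through.** **1. The sections side by side.**

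| Situation after withdrawal | Contact under 8.3-8.4 | Recording under 10.7 |
|---|---|---|
| Event that caused withdrawal | Followed until resolved or stable | Inside the window |
| New event within 30 days | Visits or calls | Inside the window |
| New event after 30 days, child still attends | Evaluations, possibly limited | Outside on the natural reading; arguably inside if visits are not yet complete |
| New event after 30 days, telephone only | Calls with no stated schedule, content or end | Outside |

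The natural reading of 10.7 gives completers one end date and withdrawn children another. The conflict lies in the last two rows.

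**2. Time outside the window for one child.** Inputs: a 24-month horizon (section 3) and a limit of 30 days, taken as 1 month (10.7). The withdrawal month *w* is assumed. For a child infused at baseline, months outside = 24 - *w* - 1.

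- *w* = 3: 24 - 4 = 20 months, 20/24 = 83%
- *w* = 6: 24 - 7 = 17 months, 17/24 = 71%
- *w* = 12: 24 - 13 = 11 months, 11/24 = 46%

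These are months outside the stated recording window, not months without any observation.

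**3. Effect on what the trial can show.** Section 3 says 30 subjects allow assessment of SAEs with 10 to 15% incidence, but it attaches no probability, so there is no plan figure to reproduce. With 2:1 allocation, about 30 x 2/3 = 20 children receive cells at baseline. The chance of seeing at least one event is 1 - (1 - p)^n. The exact two-sided 95% upper limit with zero events is 1 - 0.025^(1/n).

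| Children observed for late events | p = 10% | p = 15% | Upper limit, zero events |
|---|---|---|---|
| 20 | 0.878 | 0.961 | 16.8% |
| 18 (2 lost, assumed) | 0.850 | 0.946 | 18.5% |
| 15 (5 lost, assumed) | 0.794 | 0.913 | 21.8% |

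Loss of numbers alone has a modest effect.

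**4. Effect if the loss is informative.** Assume that 2 of 20 withdraw, that late risk is 10% in the 18 who stay and 30 to 50% in the 2 who leave, and that nothing late is recorded for those 2.

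- True rate: (18 x 0.10 + 2 x 0.30)/20 = 12%, up to (18 x 0.10 + 2 x 0.50)/20 = 14%
- Expected rate among those who stay: 10%
- Expected rate if the 2 are counted as event-free: 18 x 0.10/20 = 9%

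Every withdrawal count and risk here is an assumption. The calculation shows the mechanism and does not predict this trial.

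**The case against.** A reader might infer that children withdrawn for harm simply vanish from the 2-year safety objective. The documents do not support that, for four reasons.

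- The event that prompts withdrawal precedes it and is recorded. For time to first SAE, a child withdrawn because of an SAE is already an event, not a censored case.
- New lesions and neurological decline are found by imaging and examination as well as through adverse event forms. The 1-year column of Appendix A, on which the end-of-study evaluation is modelled, includes physical examination, videotaped evaluation, DT-MRI and AE/SAE evaluation.
- Section 10.4 sends all deaths and all hospitalizations for infection or neurological events to the Medical Safety Monitor, and 10.9.1 times reports of deaths and infusion-related SAEs from discovery. Neither states a 30-day limit.
- Children whose infusion is stopped (10.8) or cannot be given (6.2.1) stay in follow-up.

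Section 10.7 can also be read more generously: a withdrawn child who keeps attending has not completed study visits, so recording continues.

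All of this stands, and it narrows the point without removing it. The generous reading makes 10.7 ambiguous and does not clearly cover a child followed only by telephone. Continued evaluations may be limited, and no 24-month examination or MRI is assured after withdrawal. Reporting to the monitor does not replace entry in the trial data. A child withdrawn for a non-serious event, an abnormal laboratory result or deterioration that is not an SAE has not yet had an SAE and could still be censored at raised risk.

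**Conclusion.** The point holds in a limited form. Section 10.7 conflicts with 8.3 and 8.4, or is at best ambiguous beside them. The gap is confined to new or recurrent events learned of more than 30 days after withdrawal and is clearest for telephone-only follow-up. Censoring in the late safety rates and the 9.1.1 estimates could be informative, because withdrawal can be caused by deterioration or an adverse event.

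The overall size cannot be derived, since the documents give no withdrawal rate or timing. The firm figure is per child: withdrawal at month 6 after a baseline infusion leaves about 17 of 24 months outside the window.

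Two further inferences should be resisted. One is that the lost time is concentrated in children withdrawn for harm: 8.2 also lists non-compliance, loss to follow-up, investigator discretion and parental request. The other is that the late rates are known to be biased toward safety: that needs a higher late risk in withdrawn children, which is plausible but not shown. Section 9.1.1 also does not say that follow-up is censored at withdrawal plus 30 days; that would be an inference from 10.7.

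**What to change.** Reconcile 10.7 with 8.3 and 8.4. For every child who received cells or placebo, record AEs and SAEs to the planned 2-year date regardless of withdrawal, unless the parent refuses further contact. Use the continued evaluations and telephone calls already foreseen. In 9.1.1, state that time-to-SAE follow-up ends at the last safety contact, and report reasons for withdrawal beside the late safety results.

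The cost is a short amendment to 10.7, a matching line in 9.1.1 and case report form guidance. The calls need a stated schedule, adverse event content and an end date, which 8.4 does not now give, so this takes somewhat more than one sentence. Otherwise the burden is a few more adverse event entries.

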10.7.1 Grading Criteria

The severity of adverse events experienced by the subjects will be graded according to the criteria set forth in the National Cancer Institute's Common Toxicity Criteria for Adverse Events Version 4.0. This document (CTCAE v4.0) provides a common language to describe levels of severity, to analyze and interpret data, and to articulate the clinical significance of all adverse events.

Adverse events will be graded on a scale from 1 to 5 according to the following standards in the NCI-CTCAE:

Grade 1 = mild adverse event

Grade 2 = moderate adverse event

Grade 3 = severe and undesirable adverse event

Grade 4 = life-threatening or disabling adverse event

Grade 5 = death

10.7.2 Attribution Definitions

The relation, or attribution, of an adverse event or experience to the investigation product will be determined by the principal investigator and will be recorded on the CRF. The relation of an adverse event to the treatment will be determined according the definitions in the NCI-CTCAE.

10.8 Termination of the Cellular Product Infusion

If at any point during the cellular product infusion (BMMNCs or hUCB) the subject experiences symptoms associated with anaphylaxis (such as wheezing, blood pressure changes, rash, vomiting), the infusion will be stopped. The subject will continue to be enrolled and followed in the study through 2 years.

10.8.1 Stopping Rules

- 1. ANY death that is deemed by the DSMB to be related or possibly related to the study treatment.
- 2. Both P:F ratio < 70 AND PaC02 > 90 within the first 48 hours post BM infusion occurring in a single subject.
- 3. AST/ALT > 900 U/dl in the first 24 hours post infusion occurring in a single subject.
- 4. Grade 4 5 CNS cerebrovascular ischemia event or Grade 4 5 seizure event as defined in the NCI CTCAE v4.0 occurring within 12 hours of BMMNCs or Cord blood Cell re-infusion.
- 5. Any Grade 4 5 Adverse Event as defined in the NCI CTCAE v4.0 and determined to be temporally-related by the Medical Safety Monitor and/or DSMB.

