6.2.2 Pulmonary Complications

A concern exists regarding the systemic infusion of leukocytes in a concentrated manner. Theoretically, activated monocytes could function to enhance polymorphonuclear leukocytes (PMN) migration into the lung, as the lung is the primary "first pass" filter for intravenous infusion of any cellular product. PMN mediated organ injury typically occurs over a 6 – 24 hour time frame. Based on this, chest radiographs will be performed and evaluated at Baseline and on Post-Infusion Day 1. Additionally, blood-oxygen saturation will be monitored by finger pulse oximetery (SpO₂). Moderate respiratory dysfunction within the first 24 hours post – infusion will be considered an adverse event but will not warrant stopping the trial unless recommended by the DSMB. In the event of pulmonary dysfunction, standard supportive therapy will be given. Pulmonary symptoms/events corresponding to the CTCAE v4.0 Grade 3 will trigger the stopping rules described in section 10.

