10.9 Communication and Reporting Serious Adverse Events (SAEs)

Any grade 4-5 adverse event (CTCAE v4.0) deemed by the MSM and/or the DSMB to be temporally associated with the treatment will prompt cessation and trigger the stopping rules. Triggering the stopping rules will prompt notification of the FDA and IRB. If a patient that receives study treatment dies, and the DSMB determines that it may be related to the treatment, then the study will be terminated and a comprehensive safety review undertaken.

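### Stopping rule 2, the only pulmonary stopping rule with numeric limits, is worded for bone marrow infusions only and leaves out every child given cord blood cells

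*Combined protocol and SAP*

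**What the plan says.** Rule 2 in section 10.8.1 requires a P:F ratio below 70 and a PaCO2 above 90, both "within the first 48 hours post BM infusion occurring in a single subject".

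The other four rules in the list are not limited to one product:

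- Rule 1 covers any death judged related or possibly related to study treatment.
- Rule 3 (liver enzymes) applies "in the first 24 hours post infusion occurring in a single subject" and names no product.
- Rule 4 (cerebrovascular ischaemia or seizure) names both products: "occurring within 12 hours of BMMNCs or Cord blood Cell re-infusion".
- Rule 5 covers any Grade 4-5 event "determined to be temporally-related by the Medical Safety Monitor and/or DSMB".

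Section 10.8, directly above the list, names both cell products when it describes stopping an infusion. Section 6.2.2 describes the lung as the first-pass "filter for intravenous infusion of any cellular product" and adds: "Pulmonary symptoms/events corresponding to the CTCAE v4.0 Grade 3 will trigger the stopping rules described in section 10". Section 10.9 repeats the Grade 4-5 provision for events "deemed by the MSM and/or the DSMB to be temporally associated with the treatment". Section 1.1 makes pulmonary function part of the primary safety outcome and does not separate the products.

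**The concern.** The trial's primary objective is the safety of two cell products, yet its one objective pulmonary stopping criterion is written for only one of them. In a marrow child, the two blood-gas values are enough to meet the rule. In a cord blood child, the same values count only if someone judges the event temporally related (rule 5 and 10.9), or if staff apply a Grade 3 trigger that sits in 6.2.2 and does not appear in the 10.8.1 list.

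A rule that can be triggered by a single subject has to be unambiguous when it is applied, and 10.8.1 is the list that staff and the DSMB will consult. As written, the two products have different pulmonary triggers with no stated reason.

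**Working it through.** The point rests on wording, and the plan gives no figure to reproduce. The check has three steps.

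**Step 1: is BM a shorthand for cells in general?** Compare the five rules in 10.8.1.

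| Rule | Event | Product wording | Covers cord blood? |
|---|---|---|---|
| 1 | Related or possibly related death | Study treatment | Yes |
| 2 | P:F < 70 and PaCO2 > 90, 48 hours | BM infusion | No |
| 3 | AST/ALT > 900, 24 hours | Infusion, no product named | Yes |
| 4 | Grade 4-5 ischaemia or seizure, 12 hours | Both products named | Yes |
| 5 | Grade 4-5 event judged temporally related | No product named | Yes |

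One rule of five is limited to one product. Elsewhere in the list, and in 10.8, the protocol either names both products or stays neutral. BM is therefore not a consistent shorthand.

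**Step 2: does the protocol's rationale support a marrow-only rule?** It does not.

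- Section 6.2.2 attaches the lung risk to cellular products generally.
- Section 3 sets the marrow dose at 6×10⁶ cells/kg and allows cord blood from 2×10⁶ to 10×10⁶ cells/kg, aiming for the most available within that range. A cord blood child's load per kg can therefore reach 10/6 ≈ 1.7 times the marrow dose.
- Sections 5.1.7 and 5.2.9 prescribe the same chest x-ray and finger oximetry in both arms.

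**Step 3: how many children does the clause omit?**

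Inputs: 30 subjects, 15 per product arm, allocated 2:1 treatment to sham (section 3; 2:1 also in 5.1.2 and 5.2.5); sham children may receive cells at one year (5.1.8, 5.2.10).

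- Cells at baseline, per arm: 15 × 2/3 = 10. Sham, per arm: 15 × 1/3 = 5.
- First randomised to cells: 10 + 10 = 20, of whom 10 receive cord blood: 10/20 = 50%.
- With full cross-over, cord blood infusions: 10 + 5 = 15. All cell infusions: 20 + 5 + 5 = 30. Share outside rule 2: 15/30 = 50%.

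The corrected wording would bring these 10 to 15 children under rule 2. Sample size, alpha and power do not change.

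**The case against.** The strongest reply is that cord blood children lose almost no real protection.

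- **Section 6.2.2** has a pulmonary trigger at a lower threshold, Grade 3, which names no product and needs no judgement of temporal relation. A child with P:F below 70 and PaCO2 above 90 would ordinarily have met it already.
- **Rule 5 and 10.9** cover any temporally related Grade 4-5 event. For life-threatening respiratory failure within 48 hours of an infusion, the timing is nearly self-evident, and the MSM reviews SAEs in real time (10.4, 10.6.1).
- **Blood gases are not scheduled** in either arm in Appendix A, so rule 2's values would be obtained only in a child already critically ill.
- **Rule 2 states no action.** Section 10.9 ties cessation to Grade 4-5 events judged temporally associated, so calling rule 2 automatic is partly an inference.
- **BM may be a drafting slip**, which would call for an editorial correction only.

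Much of this stands. The practical gap is small, and cord blood children are not without a pulmonary stop. It does not make the wording adequate, for three reasons.

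First, 6.2.2 refers the reader to section 10, but the 10.8.1 list has no Grade 3 rule. Its only specific pulmonary entry is rule 2, so the cross-reference is least clear for the children rule 2 omits. The mismatch between Grade 3 in 6.2.2 and the thresholds in 10.8.1 is a separate inconsistency.

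Second, rule 5 depends on a judgement that rule 2 does not need. Section 10.9.1 allows five days for infusion-related SAEs to reach the MSM, and the DSMB charter allows seven calendar days for unexpected, related SAEs to reach the DSMB. Section 5.2.9 calls for immediate reporting, so delay is possible but not certain.

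Third, it is fair to read an item headed as a stopping rule, with no relatedness condition attached, as operating on the values alone. If BM is a slip, it is a slip in an operative safety rule and still needs correcting.

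**Conclusion.** The concern holds. Rule 2 is the only one of the five stopping rules limited to one product and the only one with numeric pulmonary limits. It excludes cord blood recipients without a stated reason and against the rationale in 6.2.2. It omits 10 of the 20 children first randomised to cells, and 15 of 30 cell infusions if all sham children cross over.

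The counts assume full enrolment and exact 2:1 allocation within each product arm. They measure coverage, not risk: the documents give no rate for this event, so no expected number of missed stops can be calculated. The practical consequence is limited, because Grade 4 is defined in 10.7.1 as life-threatening and such a child would ordinarily meet rule 5. What cord blood children lack is the objective trigger that needs no judgement. The correction should be made because the rule, as written, is wrong for one arm of a safety trial.

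**What to change.** In rule 2 of section 10.8.1, replace BM with BMMNC or hUCB. Keep the 48-hour window, the single-subject condition and both numeric limits, and continue to obtain blood gases for cause only. If the sponsor does intend the rule for marrow alone, add a sentence to 10.8.1 giving the reason.

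The cost is one phrase in one rule, with no added procedure, visit or sample. The one downside is that the cord blood arm gains a further automatic trigger, so the trial could be halted by an event that would otherwise have gone first to the MSM or DSMB for judgement.

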4.2 Exclusion Criteria

- 1. Known history of:
 - a. Intractable seizures
 - b. Traumatic brain injury
 - c. Genetic disorder (as demonstrated by newborn screening or genetic diagnostic testing)
 - d. Recently treated or current infection
 - e. Renal insufficiency or altered renal function (as defined by serum creatinine > 1.5 mg/dl at screening)
 - f. hepatic disease or altered liver function (as defined by SGPT > 150 U/L [non-contusion related], and/or T. Bilirubin >1.3 mg/dL at screening)
 - g. HIV+ (as demonstrated by positive blood test)
 - h. Immunosuppression (as defined by WBC <3,000 cells/ml at screening)
 - i. Infectious related neurological injury
 - j. Sensitivity to Ethylene Oxide (EtO) [found in fumigants and disinfectants]
- 2. If Athetoid CP diagnosis, other etiologies such as degenerative, mitochondrial, and metabolic disorders must be excluded, and the outcome assessments must be able to be conducted to assess for potential treatment effects

- 3. Normal brain MRI
- 4. Evidence of acute illness at the time of infusion, such as, but not limited to, fever (temperature > 37.5 C), vomiting, diarrhea, wheezing or crackles
- 5. Progressing neurological disease (as defined by Batten Disease, Leukodystrophies, Metabolic disorders, Mitochondrial disorders, Neurotransmitter disorders)
- 6. Microcephaly, macrocephaly, cortical malformations, genetic disorders of dysgenesis brain malformations due to infection or metabolic disorders
- 7. Pulmonary disease requiring ventilator support
- 8. If hUCB candidate, banked cord cells totaling <10 million/kg
- 9. If hUCB candidate, any positive maternal infectious disease test (Hepatitis A/B, HIV 1, HIV 2, HTLV 1, HTLV 2, and Syphilis), (refer to Appendix D)
- 10. If hUCB candidate, cord blood sample contamination
- 11. Participation in a concurrent interventional research study
- 12. Unwillingness to return for follow-up visits
- 13. Contraindications to brain MRI (metal implants, dental braces, etc.)
- 14. Any subject that the investigators, feel in their opinion the study intervention is unlikely to benefit the subject will be a screen failure
- 15. Previous participating in other stem cell treatment or research studies

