6.2.3 Hepatic Injury

The reticuloendothelial system can sequester immature blood elements, theoretically resulting in hepatic injury. An acute elevation of the AST/ALT hepatic enzymes > 900 U/dL in the first 24 hours post – infusion will trigger the stopping rules. This level is corresponds to the CTCAE v4.0 Grade 4 adverse event. It is unlikely that "end vessel" microthrombosis would occur in the liver due to the dual blood supply of the liver and the lung is the first pass organ.

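### The liver-enzyme stopping rule is set per decilitre, so as written it fires only above 9,000 U/L, ten times the value probably meant.

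*Combined protocol and SAP*

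**What the plan says.** The protocol defines the hepatic trigger in two places. Rule 3 of section 10.8.1 reads "AST/ALT > 900 U/dl in the first 24 hours post infusion occurring in a single subject". Section 6.2.3 sets the same trigger at "AST/ALT hepatic enzymes > 900 U/dL in the first 24 hours" and adds: "This level is corresponds to the CTCAE v4.0 Grade 4 adverse event". Both use units per decilitre, and no other section restates the trigger in another unit.

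The entry criterion uses a different unit for the same enzyme. Section 4.2 excludes children with "hepatic disease or altered liver function (as defined by SGPT > 150 U/L" at screening (SGPT is ALT).

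Two further provisions can stop the trial for a liver event. Rule 5 of section 10.8.1 covers any Grade 4 or 5 event that is "determined to be temporally-related by the Medical Safety Monitor and/or DSMB". Section 10.9 covers Grade 4 or 5 events "deemed by the MSM and/or the DSMB to be temporally associated with the treatment will prompt cessation". Section 10.6.1 adds a general safeguard: "All safety data will be reviewed by the Medical Safety Monitor (MSM) in real time".

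Liver function is also part of the primary safety outcome in section 1.1: "In-hospital infusion toxicity: pulmonary and hepatic function".

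**The concern.** A numeric stopping boundary should have one reading. This one has two, a factor of ten apart: the literal reading, 9,000 U/L, and the probable intended reading, 900 U/L. Because the same unit appears in 6.2.3 and in 10.8.1, neither place corrects the other.

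Rule 3 is the only stopping rule that carries a liver enzyme value. It needs one result in one child and lists no attribution step. If the literal unit is applied, a child whose enzymes reach several thousand U/L within a day of infusion does not meet it. The decision to stop then depends on how the event is graded and judged. The children are 2 to 10 years old, and hepatic function is a named primary in-hospital safety measure, so the boundary should be unambiguous.

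**Working it through.** **Inputs**

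- Trigger: AST/ALT above 900 U/dL in the first 24 hours, single subject (10.8.1 rule 3; same value in 6.2.3).
- Entry limit: ALT (SGPT) above 150 U/L excludes (4.2).
- Conversion: 1 L = 10 dL, so a value in U/L is 10 times the value in U/dL.

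The protocol does not derive the figure of 900, and it gives neither an upper limit of normal (ULN) nor the CTCAE multiple for Grade 4. The threshold therefore cannot be reproduced from its own inputs; only its unit can be checked.

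**Conversion and ratio to the entry limit**

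- As written: 900 U/dL × 10 dL/L = 9,000 U/L; 9,000 / 150 = 60 times the entry limit.
- If U/L was meant: 900 / 150 = 6 times the entry limit.
- Entry limit in the trigger's unit: 150 / 10 = 15 U/dL.

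**Rule 3 at test values under each reading**

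| Result (U/L) | Same result (U/dL) | Fires as written (> 900 U/dL) | Fires if unit is U/L (> 900 U/L) |
|---|---|---|---|
| 150 | 15.0 | no | no |
| 500 | 50.0 | no | no |
| 901 | 90.1 | no | yes |
| 2,000 | 200.0 | no | yes |
| 5,000 | 500.0 | no | yes |
| 9,000 | 900.0 | no | yes |
| 9,001 | 900.1 | yes | yes |

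The two readings disagree for every value above 900 and up to 9,000 U/L, a band 9,000 − 900 = 8,100 U/L wide.

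**Which reading is plausible?** This step needs a ULN, which the documents do not give. Assume 30 to 60 U/L:

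- 900 U/L is 900/60 = 15 to 900/30 = 30 times ULN.
- 9,000 U/L is 9,000/60 = 150 to 9,000/30 = 300 times ULN.

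The first range is much the more natural place for a stopping threshold. That supports U/L as the intended unit but does not prove it.

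**What covers the band in which rule 3 is silent**

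| Provision | Needs a Grade 4–5 classification | Needs a judgement of temporal relation |
|---|---|---|
| Rule 3 (10.8.1) | no | no |
| Rule 5 (10.8.1) | yes | yes, by the Medical Safety Monitor and/or DSMB |
| Section 10.9 | yes | yes, by the Medical Safety Monitor and/or DSMB |

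There is also a step before grading. Under section 10.7 an abnormal result is recorded as an adverse experience if the investigator considers it clinically significant or temporally related.

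**The case against.** The strongest reply is that nobody will apply the literal reading. Entry uses U/L. To be misled, staff would have to take a result reported in U/L, convert it to U/dL and then compare it with 900, and nothing in the protocol suggests they would. Section 6.2.3 also ties the level to a published grade, so the intended value can be looked up. On this view the factors of 60 and ten describe a literal reading, not a likely effect on the trial.

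The safeguards are also substantial. Rule 3 covers only the first 24 hours, and judging that an event in that window is temporally (not causally) related is a low hurdle. Hepatic indices are monitored after infusion, the team reviews the first 24 hours before discharge (5.1.7 and 5.2.9), and the Medical Safety Monitor reviews safety data as they arise. The unit changes no estimate, power figure or analysis. The protocol does not itself call rule 3 automatic, and the link to stopping that 10.9 spells out is for Grade 4 or 5 events judged temporally associated.

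Most of this stands, and it limits the consequence: the ability to stop is not lost, and U/L is the likely intent. It does not remove the error. The wrong unit is in both places that define the rule, and a stopping rule should not rely on readers silently replacing its unit. The safeguards work only if the value is graded 4 or 5 and then judged related. Rule 3 lists neither condition, and in that sense it is automatic.

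**Conclusion.** The concern holds and should be fixed. As written, the hepatic trigger is 9,000 U/L, ten times the probable intended value and 60 times the entry limit. Results above 900 and up to 9,000 U/L in the first 24 hours do not fire rule 3.

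What is lost in that band is the single-subject numeric trigger that needs no judgement. Stopping through rule 5 or section 10.9 remains possible, and review by the Medical Safety Monitor continues.

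The conversion and the mismatch with the entry unit rest on the documents alone. That U/L was intended is an inference from the entry unit and the claimed Grade 4 level, helped by the assumed ULN of 30 to 60 U/L. Whether 900 U/L really is the Grade 4 level for this laboratory cannot be settled from the documents.

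**What to change.** Replace U/dL with U/L in section 6.2.3 and in rule 3 of section 10.8.1. Before doing so, confirm the laboratory's reporting unit and reference range, and check that 900 U/L matches the CTCAE v4.0 Grade 4 level that 6.2.3 claims. If it does not match, put the correct Grade 4 value in U/L in both places.

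The cost is a unit correction in two places and one check against the reference range. No visit, sample or procedure is added.
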